1.4 Study Objectives

- a) Primary Objective:
 - To evaluate the washout PK of RAL in infants born to pregnant women with HIV1 infection receiving RAL during pregnancy.
 - To evaluate bilirubin levels and the safety of in utero/intrapartum exposure to RAL in infants born to pregnant women with HIV1 infection receiving RAL during pregnancy.

- To develop a neonatal RAL dosing regimen to be evaluated in a follow-up study of this protocol.

b) Secondary Objective:

- To investigate the relationship between neonatal RAL elimination and UGT1A1 genotype.

1.5 Outcome Measures

a) For primary objectives:

- PK outcome measures:
 - Neonatal RAL elimination ($T_{1/2}$).
 - RAL maternal-cord blood ratio (for Cohort 1 only).
- Safety outcome measures:
 - Infant adverse events (AEs) of Grade 3 or 4 as defined in DAIDS Table for Grading the Severity of Adult and Pediatric Adverse Events (DAIDS AE Grading Table), Version 1.0, dated December 2004, Clarification August 2009, which is available on the RSC website at <http://rsc.tech-res.com/safetyandpharmacovigilance>.
 - **Adverse birth outcomes including stillbirth and low birth weight^a (for Cohort 1 only)**
 - Infant death
 - Total bilirubin
 - Direct bilirubin

^a **Prematurity and growth restriction are highly linked to LBW and will be considered baseline AEs for Cohort 2.**

b) For secondary objective:

- Neonatal RAL elimination (concentrations and $T_{1/2}$)
- UGT1A-1 genotype (presence or absence of *28/*28 genetic variant)

2 SMC Monitoring of Cohort 2

Cohort 1 was fully accrued under Protocol Version 1.0. The SMC report will not include any data from Cohort 1.

Cohort 2 will be monitored for accrual by a Study Monitoring Committee (SMC) to be appointed per IMPAACT Standard Operating Procedures. The SMC will assess accrual 6 months after Cohort 2 opens to enrollment and Protocol Version 2.0 has been approved by IRB/ ECs at 50% of eligible sites, and perform an independent review of the data. If Cohort 2 has not met the accrual target subjects (7 PK evaluable infants) by the 6-month timeframe, the protocol team will be required to provide a written plan to increase accrual prior to the SMC 6-month review at which time the SMC will consider whether to recommend closing the study to enrollment.

A summary of P1097 Cohort 2 administrative data will be included in the SMC report which will be prepared by the protocol statisticians. Other than the site activation summary table, the rest of the summary tables below will be generated by the protocol statisticians.

- Site activation
- Accrual (M-I pairs, Infants, PK evaluable infants)
- Eligibility verification
- Study status

3 Statistical Principles

3.1 General Consideration

Cohort 1 was closed under Version 1.0 with final analysis report for Cohort 1. Data analysis is done separately for the two cohorts and no across cohort analysis will be done.

For Cohort 1, team pharmacologists decided if infants were PK evaluable or not. For Cohort 2, the washout PK analysis will be based on infants from whom at least 3 neonate blood specimens were collected from the first 5 time points (PK analyses will be done by the protocol pharmacologist). PK unevaluable infants will still remain in the study and will be followed for safety.

3.2 Infant Safety Data Collection Schedule and Visit Windows

Table 1 shows the Schedule of Evaluations (SoE) for safety data and includes definition of “wide” visit windows to be used for checking availability of safety data. **Any AEs after the cut-off day for the last study visit will not be in summary tables, but will be mentioned in the report.**

Table 1: Infant Safety Data Collection Schedule and Visit Windows

Evaluation	Scheduled visits					
	Entry/Birth (0 hour after birth)	36 - 48 hours after birth	72 - 84 hours after birth	Week 1 (7 – 14 days after birth)	Week 6 (34 - 49 days after birth)	Off Study
	0-1 day	2 days	3-4 days	5-21 days	22-56 days	
Hematologies and liver chemistries (LBW0093) ³		X ¹	X ²	X		
Signs and Symptoms (PE6831)	X	X		X	X	X
Diagnoses (PE6851)	X	X		X	X	X

¹ Required at this visit: hematology and bilirubin. Hematology to include CBC with differential and platelet count. Bilirubin to include Total and Direct.

² Required at this visit: chemistry. Chemistry includes AST, ALT, Creatinine, Total Bilirubin and Direct Bilirubin.

³ Hematologies and liver chemistries have specimen date and time records. Detailed specimen time data would contribute to data completeness analysis if needed.

3.3 Statistical Tests and Analytic Approaches

3.3.1 Safety Analysis

The safety analysis will consist of descriptive statistics summarizing the safety data from all enrolled infants, including infants who were not evaluable for the washout pharmacokinetic analysis.

The composite infant primary toxicity endpoint has the following components:

- Infant AEs of Grade 3 or 4; or
- **Adverse birth outcomes including stillbirth and low birth weight (for Cohort 1 only)^a ;**
or
- Infant death

^a **Prematurity and growth restriction are highly linked to LBW and will be considered as baseline events for Cohort 2. Cohort 2 baseline events will be summarized separately and will be excluded from the AE tables.**

The primary safety analysis will be the calculation of the point and 2-sided 90% confidence interval (CI) using the Clopper-Pearson exact method estimates of the proportion of infants meeting the composite toxicity endpoint.

To show additional details relating to the analysis of the composite infant safety endpoint, the following will be generated: (1) point and 90% Clopper-Pearson CI estimates of infants meeting each component of the composite toxicity endpoint; (2) frequency tabulations of worst grade adverse events for each subject; and (3) listing of reasons for infant death.

To summarize bilirubin-related data, the following will be generated: (1) summary statistics for total and direct bilirubin at each required sampling time; and (2) point and 90% Clopper-Pearson CI estimates of proportion of infants requiring therapy (e.g. phototherapy, exchange transfusion) to reduce bilirubin.

3.3.2 Secondary Study Objective Analysis

Neonatal RAL elimination ($T_{1/2}$) for infants with versus without polymorphisms on UGT1A1 will be summarized using summary statistics and the comparison of median for these groups will be done using the Wilcoxon Sum Rank Test ($\alpha=0.05$). Analysis will be limited to infants with non-missing RAL elimination and UGT1A1 polymorphism data. There may be limited statistical power for this analysis if there is small sample size.

4 Report Contents

Detailed descriptions of the content of each of the following sections are given in the AIP.

- 1) Accrual (M-I pairs, Infants, PK evaluable infants) and eligibility criteria violations**
- 2) Baseline characteristics**
- 3) Study status**
- 4) Data completeness**
- 5) Safety data**
- 6) Neonatal RAL elimination and UGT1A1 genotype**

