- **Infant not receiving disallowed medications described in Section 4.8. If these medications are required for the infant's care, the infant will be ineligible for further PK (pharmacokinetic) sampling. Data will be obtained up to the time of the introduction of the disallowed medication, but such infant will not be considered one of the evaluable 15 infants.**
- **Infant \leq 48 hours of age.**

Blood samples for raltegravir assay will be collected at 1-6, 12-24, 36-48, 72-84, and 108-132 hours after birth, and on day 7-14. Infants may enroll up to 48 hours of age, and any pharmacokinetic samples scheduled for collection prior to the time of enrollment will be skipped and not replaced. Infants enrolling close to the 48-hour time point should have the first pharmacokinetic blood sample collected within 4 hours of enrollment (i.e., within 52 hours after birth) so that a minimum of three blood samples can be obtained for pharmacokinetic evaluation.

With regard to infant blood samples for safety/toxicity laboratory testing: In the event that the study-required study safety/lab samples have not been collected prior to enrollment, (e.g., due to infant enrolled after delivery), these must be collected as soon as possible after enrollment. To meet the primary objectives of the study, only those infants who have at least 3 pharmacokinetic blood samples collected from the first 5 time points will be considered to be evaluable.

Optional genotyping for polymorphisms of UGT1A1 **were performed on Cohort 1 infants and** will be performed **on Cohort 2** infants who undergo pharmacokinetic sampling. **The goal of the genotypic analysis** is to determine if certain polymorphisms, particularly those with the UGT1A1*28/*28 genotype have slower RAL elimination than those with the UGT1A1*1/*1 genotype. Because UGT1A1 activity is reduced in neonates, polymorphisms associated with reduced activity are likely to have a larger impact on the metabolism of raltegravir, especially those who are low birth weight.

No study-specific drugs will be given to women or infants during this study. Women will be receiving raltegravir for clinical indications outside of the study. Infants will receive standard of care antiretroviral therapy for prevention of mother-to-child transmission (PMTCT) as prescribed by their primary care physicians.

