1.3 Protocol Overview

P1097 is a multi-center clinical trial to determine the washout pharmacokinetics (PK) and safety of in utero/intrapartum exposure to raltegravir (RAL) in infants born to pregnant women with

HIV1 infection who received at least one dose of RAL 400mg within 2 to 24 hours prior to delivery.

The IMPAACT P1097 Protocol includes two cohorts of Mother-Infant (M-I) pairs:

- Cohort 1 (Fully accrued under Protocol Version 1.0): pregnant women with HIV1 infection receiving RAL 400mg twice daily for at least two weeks prior to delivery and continuing to receive ARVs during labor, and their infants.
- Cohort 2 (Opened to accrual under Protocol Version 2.0): pregnant women with HIV1 infection who received at least one dose of RAL 400mg within 2 to 24 hours prior to delivery and their low birth weight (LBW) infants.

Cohort 1 was fully accrued and closed to follow-up under Version 1.0. The protocol was amended to open a cohort for LBW infants (≤ 2500 grams at birth) in Protocol Version 2.0. The primary and secondary objectives of the protocol are the same for both cohorts. Data analysis will be done separately for the two cohorts and no across cohort analysis will be done.

Cohort 1 total accrual was 22 M-I pairs and there were 19 evaluable infants for the RAL washout PK analysis. The M-I pairs were enrolled prior to delivery. Infant blood samples for RAL assay were collected at 1-5, 8-14, 18-24 and 30-36 hours after birth. Maternal blood sample and cord blood sample were also collected during delivery. Team pharmacologists decided if infants were PK evaluable or not. PK unevaluable infants will still remain in the study and will be followed for safety.

Cohort 2 will enroll up to 20 M-I pairs to achieve 15 evaluable LBW infants for the washout PK of RAL. The M-I pairs will be enrolled prior to delivery or within 48 hours after birth. Infant blood samples for RAL assay will be collected at 1-6, 12-24, 36-48, 72-84 and 108-132 hours after birth, and on day 7-14. When possible, maternal blood sample and cord blood sample will be collected during delivery. The washout PK analysis will be based on infants from whom at least 3 neonate blood specimens were collected from the first 5 time points (PK analyses will be done by the protocol pharmacologist). PK unevaluable infants will still remain in the study and will be followed for safety.

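### SAP 3.3.2 tests half-life by UGT1A1 genotype with a rank-sum p-value alone; without a between-group estimate and interval, a non-significant result would say very little

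*SAP*

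**What the plan says.** The secondary objective (Protocol 2.2, SAP 1.4) is to relate neonatal raltegravir elimination to UGT1A1 genotype. Protocol 3.0 gives the aim a direction: whether certain polymorphisms, \*28/\*28 in particular, "have slower RAL elimination than those with the UGT1A1*1/*1 genotype".

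SAP 3.3.2 is the only place that gives an analysis method. It describes half-life in each of two genotype groups, with and without a polymorphism, by simple summaries. For the contrast between them it states that "the comparison of median for these groups will be done using the Wilcoxon Sum Rank Test". Alpha is set at 0.05, and only infants who have both data items enter. It adds: "There may be limited statistical power for this analysis if there is small sample size". It does not mention a difference, a ratio, an interval, sidedness, or exact versus asymptotic p-values. Protocol 8.22 and 9.2 add no method. SAP section 4 leaves report detail to an Analysis Implementation Plan (AIP), which is not among the documents.

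On numbers, SAP 1.3 says that Cohort 2 enrols "to achieve 15 evaluable LBW infants for the washout PK of RAL" and that in Cohort 1 "there were 19 evaluable infants for the RAL washout PK analysis". The same section rules out any analysis across cohorts. Genotyping is optional (Protocol 3.0 and 8.22).

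**The concern.** The planned output is two group summaries and a p-value. In groups this small the p-value will often exceed 0.05 whether or not genotype matters, and nothing planned shows which half-life ratios the data still allow. A null result is also realistic: Protocol 1.25 reports that half-life was not prolonged in adults with \*28/\*28. A bare p above 0.05 could then be read as evidence that genotype has no effect on neonatal elimination, when the data may be compatible with a doubling. Protocol 9.2 expects the genotype data to improve understanding of genetic effects on neonatal metabolism, and a p-value alone does little for that.

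The second point is about wording. The rank-sum null hypothesis is that the two half-life distributions are identical. It is a test of medians only if the groups differ by a shift and nothing else, and the SAP does not state that assumption.

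**Working it through.** The plan gives no sample size, power, effect size or genotype frequency for this test, so there is no figure of its own to reproduce. Alpha 0.05 is the only number.

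**Inputs from the documents.** N is at most 15 (Cohort 2) or 19 (Cohort 1). Cohort 1 half-life had a median of 26.6 h and a range of 9.3-184 h (Protocol 1.11 and 1.26).

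**Assumptions.** Half-life is log-normal with the same spread in both groups, and the test is two-sided and exact. The log-SD is the log range divided by the expected range of 18-19 standard normal values: ln(184/9.3) = 2.985, and 2.985/3.66 = 0.82. Half-life ratios of 2 and 3 are illustrative, since no document gives one. Let m be the size of the smaller genotype group. SAP 3.3.2 groups infants by any polymorphism, while SAP 1.5 defines the measure as "UGT1A-1 genotype (presence or absence of *28/*28 genetic variant". The two definitions can give different m, so a range is shown.

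**Step 1: smallest attainable p.** This is 2/C(N, m).
- m = 1, N = 15: 2/15 = 0.133. m = 1, N = 19: 2/19 = 0.105. One-sided, these are 0.067 and 0.053. No data can reach 0.05.
- m = 2, N = 15: 2/105 = 0.019, so rejection becomes possible.

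**Step 2: how likely is m of 0 or 1?** At N = 15, P(m ≤ 1) = (1−q)^15 + 15q(1−q)^14, where q is an assumed \*28/\*28 frequency.
- q = 5%: 0.463 + 0.366 = 0.83
- q = 10%: 0.206 + 0.343 = 0.55
- q = 20%: 0.035 + 0.132 = 0.17

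**Step 3: miss rates and intervals.** Miss rate is one minus simulated power of the exact test (40,000 trials per setting). The interval is the exact 95% Hodges-Lehmann interval for the half-life ratio, shown as median limits when the true ratio is 1.

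| N | Split | Missed, ratio 2 | Missed, ratio 3 | Typical 95% interval, no effect |
|---|---|---|---|---|
| 15 | 2 v 13 | 86% | 70% | 0.23-4.39 |
| 15 | 3 v 12 | 79% | 56% | 0.30-3.32 |
| 15 | 5 v 10 | 75% | 45% | 0.36-2.81 |
| 15 | 7 v 8 | 72% | 39% | 0.38-2.66 |
| 19 | 2 v 17 | 84% | 65% | 0.25-3.99 |
| 19 | 3 v 16 | 78% | 53% | 0.32-3.08 |
| 19 | 5 v 14 | 70% | 38% | 0.38-2.60 |
| 19 | 7 v 12 | 64% | 28% | 0.42-2.30 |

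With a log-SD of 0.81, the 7 v 8 miss rate at ratio 2 is 71%. At N = 15, about 71-88% of non-significant results obtained under no effect still have a two-fold longer half-life inside the interval. At m = 1 no finite 95% interval exists.

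**Step 4: the medians wording.** With equal medians, N = 15 and splits 2 v 13, 3 v 12 and 4 v 11, the rejection rate depends on how the smaller group's log-SD compares with the larger group's:
- equal spread: about 4-5%
- twice the spread: about 16%, 13% and 9%
- half the spread: about 0.5%, 1.3% and 1.7%

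The error can go either way.

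**The case against.** Several points on the other side stand.

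- **Limited power is already conceded.** SAP 3.3.2 says so, but gives no number and no way to read a non-significant result.
- **Group summaries are planned.** Medians and group sizes can be read side by side, but they carry no uncertainty for the contrast.
- **The AIP may hold more.** Plots of individual values could be there, so their absence is not established. SAP 1.2, however, places analytic approaches in the SAP and coding and table detail in the AIP.
- **The SAP is consistent with itself.** It gives exact intervals to safety proportions, but total and direct bilirubin, also continuous, get summary statistics only.

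A reader might go further in three ways that the documents do not support.

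- **That the test rejects falsely as a test of medians.** The inflated rates in step 4 need the smaller genotype group to be the more variable one. The 9.3-184 h range describes all Cohort 1 infants together, and no document says that spread differs by genotype. Nor would the proposed interval cure such an error, because it inverts the same test. Protocol 3.0 asks about slower elimination, which a rank-sum test addresses reasonably well.
- **That the genotype ratio is meant to set the follow-up dose.** Protocol 9.2 speaks only of better understanding of genetic effects. Protocol 9.3 derives the initial dose estimate from neonatal half-life and a distribution volume borrowed from P1066.
- **That the test misses most effects.** At a three-fold ratio and 7 v 8, it misses 39%.

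**Conclusion.** The concern holds as a gap in reporting. SAP 3.3.2 plans a significance test without a between-group estimate or interval, at sample sizes where a non-significant result usually leaves a doubling of half-life open and where one infant in the smaller group makes rejection impossible. The size of this rests on an assumed common log-SD of about 0.8, log-normality and the illustrative ratios. A smaller spread or a larger true effect would make the test more informative. The minimum p-value at m = 1 depends on none of these assumptions.

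The wording about medians is secondary: it is accurate only under an unstated shift assumption, and the direction and size of any error cannot be judged from the documents.

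Severity is minor. This is a secondary analysis in a pilot study, and no dose or safety decision in the documents rests on its p-value.

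**What to change.** In SAP 3.3.2:

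1. Report the Hodges-Lehmann estimate of the half-life ratio (shift on log half-life) with its exact 95% interval, beside the exact two-sided rank-sum p-value.
2. Describe the test as a comparison of half-life distributions, or state the location-shift assumption.
3. Plot individual half-lives by genotype, so that any difference in spread can be seen.
4. Interpret a non-significant result from the interval. Do not set a two-fold cut-off, since no document gives one.
5. When the smaller group has 0 or 1 infant, report descriptively only.

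The cost is SAP wording and a few lines of code, with no new data or participants. SAP 3.1 records a final report for Cohort 1, so the change matters mainly for Cohort 2. The downside is that the interval will be wide, so the result will look less definite than a p-value alone. It also relies on the same shift assumption as the test.
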